4 STUDY DESIGN

4.1 Overview

This is a Phase 1b, multi-center, open-label study with a dose-escalation part and a dose-expansion part.

The duration of the study participation for each patient is defined as the time from the date of signed written informed consent to the completion of the follow-up period, withdrawal of consent, loss to follow-up, or death, whichever occurs first.

The study will include a Screening Period (of up to 21 days), a Treatment Period (with cycles of 3 weeks for a Q3W dosing regimen), and a Follow-up Period (approximately every 12-week visits) for up to 1 year from End of Treatment (EOT) visit (Section 4.2).

See study diagram in [Appendix 13.6](#).

4.1.1 Dose-Escalation

Dose-escalation cohorts:

In the dose-escalation part, patients will receive escalating doses of camidanlumab tesirine as monotherapy, or escalating doses of camidanlumab tesirine in combination with pembrolizumab, guided by a 3+3 design.

For each dose level (Section 6.3 and Section 6.4), if none of the first 3 patients at that dose level experience a DLT, new patients may be entered at the next higher dose level. If 1 of 3 patients experiences a DLT, up to 3 more patients are to be treated at that same dose level. If none of the additional 3 patients at that dose level experience a DLT, new patients may then be entered at the next higher dose level. However, if 1 or more of the additional 3 patients experiences a DLT, then no further patients are to be started at that dose level and the preceding dose is identified as the MTD. The MTD, therefore, is defined as the highest dose level at which none of the first 3 treated patients, or no more than 1 of the first 6 treated patients, experience a DLT.

If the starting dose of camidanlumab tesirine in combination with pembrolizumab is not tolerated, two lower doses could be investigated (Section 6.4). In such cases, if a DLT is observed in the first 3 patients enrolled in dose level -1, 3 additional patients will be enrolled; if 2 DLTs are observed out of these 6 patients, dose will be de-escalated to dose level -2.

Camidanlumab tesirine as monotherapy: The DLT (see Section 6.5 for further details) observation period for dose-escalation will be 21 days following the first study drug administration.

Camidanlumab tesirine in combination with pembrolizumab: The DLT (see Section 6.5 for further details) observation period for dose-escalation will start at the time of first administration of pembrolizumab and will end 21 days following this first administration of pembrolizumab.

Different dosing schedules of camidanlumab tesirine in combination with pembrolizumab may be tested in the dose-escalation part:

- Schedule 1: Administration of camidanlumab tesirine for the first 2 cycles with concomitant administration of pembrolizumab starting at the first cycle (additional administrations of camidanlumab tesirine according to a schedule with 2 cycles off – 2 cycles on, if there is no delay in the planned treatment schedule, or, in case of delay in the administration of pembrolizumab, after respecting a minimum of 63 days (9 weeks) between the last dose of camidanlumab tesirine and the first dose of the 2 subsequent additional administrations of camidanlumab tesirine; between these Cycles, patients should receive pembrolizumab as a single agent)
- Schedule 2: Administration of camidanlumab tesirine for the first 2 cycles with concomitant administration of pembrolizumab in the second cycle followed by pembrolizumab monotherapy thereafter (additional administrations of camidanlumab tesirine upon informing the Sponsor)
- The dose-escalation part will start with Schedule 1, then:
 - Schedule 2 may be initiated if dose level -1 and dose level -2 used in Schedule 1 are presenting safety concerns (e.g., significant overlapping toxicities) and investigation of Schedule 1 is stopped.
 - Other Schedules may be investigated based on observed safety and efficacy data.

No intra-patient dose-escalation is allowed in this regular dose-escalation part of the study. The number of dose levels will depend on the emergent toxicity profile of camidanlumab tesirine and will be decided by the DESC (Section 4.1.3); PK [REDACTED] may also inform decision making.

The DESC may expand enrollment at doses below the current dose level being evaluated as part of the dose-escalation process; additional patients, of the same indication, may only be added at dose levels that are equal or higher to the dose level for which at least 1 patient with documented PR or CR has been observed. No more than 10 patients in total can be treated at such dose level unless ≥ 3 of the 10 patients have documented PR or CR.

The dose-escalation part will be completed once the recommended dose(s) (and schedule[s]) for expansion (RDE)/MTD has been identified. Dose-escalation cohorts may enroll approximately 48 patients.

Paired-biopsy cohorts: Separately, paired-biopsy cohorts will enroll patients, only treated with camidanlumab tesirine as monotherapy, who will be undergoing two mandatory biopsies, one pre- and one on-treatment biopsy, [REDACTED]

[REDACTED]. These cohorts will be introduced at dose levels that have been deemed safe during escalation and will be composed of a maximum of 3 patients per dose level, irrespective of the indication and whether or not preliminary antitumor response(s) were seen at that dose level. In order to allow patients to benefit from trial participation, one intra-patient dose-escalation (after the mandatory on-treatment biopsy has been obtained) to the highest dose level determined to be safe at that point will be performed, unless deemed by the

Investigator not to be in the best interest of the patient. Paired-biopsy cohorts may enroll approximately up to 17 patients.

Overall, Part 1 may enroll approximately 65 patients.

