4.1.3 Safety Oversight by the Dose-Escalation Steering Committee

A DESC will be responsible for safety monitoring and overall supervision of the study. Membership of the DESC will include:

- Medical Monitor(s) (Sponsor and/or designee)
- Investigator(s) from each participating site
- *Ad hoc* members (e.g., project manager, study coordinator(s), regulatory representative(s), pharmacovigilance representative(s), biostatistician(s), clinical pharmacologist(s), etc.)

In general, the DESC will make any substantial decisions regarding the conduct of the study, such as:

- Monitor the safety of the study and review its progress at monthly intervals or more frequent intervals as required.
- Determine dose levels to be administered and the RDE/MTD based on assessment of safety findings in all patients and determination of DLTs in dose-escalation cohorts.
- Provide input into protocol changes, when required.
- Determine if it is appropriate to maintain a Q3W schedule or test other dosing regimens.
- Determine whether adjustment in timing of on-treatment biopsy and other [REDACTED] sample(s) is needed based on emerging evidence.

Each DESC meeting and the decisions made will be documented in writing and provided to all participating DESC members and Investigators. Meeting documents may be submitted to IRBs/IECs or competent authorities according to institutional or local requirements.

The DESC may be maintained during Part 2 (expansion) of the study to continue to monitor and evaluate patient safety, but the frequency of meetings can be adjusted.

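### Protocol Section 4.1.1: read literally, the combination dose level -1 rule enrols 3 more patients after 2 or 3 of the first 3 have a DLT, when the level can no longer meet the MTD definition; exactly one is almost certainly meant

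*Protocol*

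**What the plan says.** Protocol Section 4.1.1 gives a general 3+3 rule and then a separate sentence for the combination's lower dose levels.

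- **General rule.** It begins "For each dose level (Section 6.3 and Section 6.4), if none of the first 3 patients at that dose level experience a DLT", in which case the next higher level may open. It continues: "If 1 of 3 patients experiences a DLT, up to 3 more patients are to be treated at that same dose level". One or more DLTs among the additional 3 closes the level. Nothing is said about 2 or 3 DLTs among the first 3.
- **MTD definition.** The MTD is the highest level at which none of the first 3 patients, or "no more than 1 of the first 6 treated patients, experience a DLT".
- **Lower levels.** If the combination starting dose (30 µg/kg, Table 5) is not tolerated, "two lower doses could be investigated". At level -1 (20 µg/kg), "if a DLT is observed in the first 3 patients enrolled in dose level -1, 3 additional patients will be enrolled"; then "if 2 DLTs are observed out of these 6 patients, dose will be de-escalated to dose level -2".
- **After level -2.** "Schedule 2 may be initiated if dose level -1 and dose level -2 used in Schedule 1 are presenting safety concerns".
- **Oversight.** Under Section 4.1.3 the DESC sets dose levels and the RDE/MTD "based on assessment of safety findings in all patients and determination of DLTs in dose-escalation cohorts". No DLT count is attached to that task.

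The SAP (Section 3) repeats the 3+3 label and adds no decision rule.

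**The concern.** The level -1 condition, that a DLT is observed, is also true when two or three are observed. The instruction that follows is mandatory, and the only written route to level -2 is counted over six patients. A site following the sentence as written would therefore enrol a second cohort after 2 or 3 of the first 3 patients had a DLT. Those patients would be treated at a dose that has already failed, and their results could not change the decision.

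Only patient safety is at stake, in a branch that opens after the combination has already proved too toxic at 30 µg/kg.

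**Working it through.** The plan states no operating characteristics for its 3+3 rule, so there is no figure to reproduce.

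**Step 1. Can the level still qualify?** Compare the number of patients with a DLT in the first 3 with the MTD definition.

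| DLT patients in first 3 | Possible total of 6 | MTD definition reachable? | General rule | Level -1 sentence, literal |
|---|---|---|---|---|
| 0 | not needed | yes (0 of 3) | escalate | not triggered |
| 1 | 1 to 4 | yes (if 1 of 6) | up to 3 more | 3 more |
| 2 | 2 to 5 | no | silent | 3 more |
| 3 | 3 to 6 | no | silent | 3 more |

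In the last two rows the second cohort cannot rescue the level.

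**Step 2. Does another numeric rule prevent it?**

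- Section 4.3.2 stops the combination for two or more cases of polyradiculopathy/GBS at diagnostic certainty Level 1. After 10 patients it also stops if at least 30% have a specific non-hematologic event of Grade 4 or higher. It halts enrolment for a Grade 5 event or two non-hematologic Grade 4 events where a drug relationship cannot be ruled out.
- Section 6.5 makes most Grade 3 non-hematologic toxicities DLTs. Two or three patients with Grade 3 DLTs can therefore occur without triggering any of these rules.
- Sections 4.1.3 and 6.4 give no DLT count.

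**Step 3. Does dose selection change?** Let p be the true DLT rate at 20 µg/kg. Level -1 meets the MTD definition with probability (1-p)³ + 3p(1-p)²·(1-p)³. Patients added after 2 or 3 of 3 do not enter this expression, so it is the same under both readings: 0.906 at p = 0.10, 0.814 at 0.15 and 0.709 at 0.20.

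**Step 4. How often could it happen?** The documents give no combination DLT rate, so every rate below is assumed. Failure at 30 µg/kg is taken as not meeting the MTD definition.

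- Failure at 30 µg/kg, rate q: F = 1 - [(1-q)³ + 3q(1-q)⁵]. This gives 0.094 (q = 0.10), 0.186 (0.15) and 0.291 (0.20).
- 2 or 3 of 3 at 20 µg/kg, rate p: G = 3p²(1-p) + p³. This gives 0.028 (p = 0.10) and 0.061 (0.15).
- Joint probability = F × G. Expected extra patients = 3 × F × G.

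| Assumed rate at 30 / 20 µg/kg | F | G | Joint | Expected extra patients |
|---|---|---|---|---|
| 10% / 10% | 0.094 | 0.028 | 0.3% | 0.01 |
| 15% / 10% | 0.186 | 0.028 | 0.5% | 0.02 |
| 20% / 15% | 0.291 | 0.061 | 1.8% | 0.05 |

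For the stated rates these are ceilings, because they take level -1 as always opened and the literal wording as always followed.

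Higher assumed rates give more: 25%/20% gives 0.400 × 0.104 = 4.2%, and 33%/25% gives 0.566 × 0.156 = 8.8%.

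**Step 5. Cost if it happens.** Three patients are treated, of whom 3p on average have a DLT: 0.30 at p = 0.10 and 0.45 at p = 0.15.

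**The case against.** The strongest reply is that the paragraph settles its own meaning. The design is called 3+3. The general rule covers each dose level in Section 6.4, whose Table 5 lists level -1, and it adds patients at 1 of 3. One DLT among the first 3 followed by two among 6 is a natural sequence; on the literal reading the second condition would already be met before the added patients were dosed. The lower doses are optional, and a DESC that reviews DLTs at least monthly would have to enrol patients at a dose its own MTD definition had rejected. It can also be said that the general rule has the same silence, and that Step 4 nevertheless treats 2 or 3 of 3 at 30 µg/kg as failure.

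Most of this stands. It makes exactly one the almost certain meaning, and it makes the harm conditional on an unlikely reading. The point about silence is also fair: the MTD definition shows that a level has failed in either place. What it does not say in either place is that enrolment stops, and at level -1 the text goes further and directs enrolment. A written dosing rule should not need the committee to override it.

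A reader might infer that the sponsor meant to dose a futile cohort, or that the risk is large. The documents support neither. Joint probabilities of 17.6% or 29.1% require DLT rates of 40%/33% or 50%/40% at 30/20 µg/kg, and nothing in the documents supports such rates. The available evidence points lower: monotherapy reached 150 µg/kg without an MTD (Section 1.3.4), and Section 2.3.2 describes a favorable safety profile for 30 µg/kg in solid tumors. How much pembrolizumab adds is unknown.

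**Conclusion.** The point holds as a minor wording defect in a safety rule. Followed to the letter, level -1 enrols 3 more patients after 2 or 3 of the first 3 have a DLT, although the MTD definition can no longer be met. The arithmetic behind that is certain; the literal reading is not the probable intent.

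The harm needs three things together: 30 µg/kg fails with pembrolizumab, level -1 is opened, and the DESC follows the literal wording. At assumed rates of 10%/10% to 20%/15% the joint probability is about 0.3% to 1.8%, rising only if pembrolizumab raises toxicity substantially. The documents do not say whether combination enrolment has already cleared 30 µg/kg; if it has, this branch should not be reached.

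It would be wrong to infer that the wording could lead to a wrong dose. The chance of accepting level -1 is identical under both readings, and no analysis changes.

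**What to change.** Make two changes in Protocol Section 4.1.1.

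1. Add to the general rule: *If 2 or more of the first 3 patients at any dose level have a DLT, no further patients are started at that level.* This closes the same gap at 30 µg/kg and above, which is reached first.
2. Replace the level -1 sentence with: *If exactly 1 of the first 3 patients at dose level -1 has a DLT, up to 3 additional patients will be enrolled; if 2 or more patients have a DLT at any point (in the first 3 or among up to 6), enrolment at that level stops and the dose is de-escalated to dose level -2.*

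The new wording also counts patients rather than DLT events, and says 2 or more where the current text says 2. The action after level -2 can stay with the DESC, as the Schedule 2 provision already allows.

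The cost is one added and one replaced sentence. No patients are added, and neither dose selection nor the SAP changes.

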The duration of the study participation for each patient is defined as the time from the date of signed written informed consent to the completion of the follow-up period, withdrawal of consent, loss to follow-up, or death, whichever occurs first.

The study will include a Screening Period (of up to 21 days), a Treatment Period (with cycles of 3 weeks for every 3 week [Q3W] dosing regimen), and a Follow-up Period (approximately every 12-week visits) for up to 1 year from end of treatment visit.

Patients may continue treatment for up to 1 year or until disease progression, unacceptable toxicity, or other discontinuation criteria, whichever occurs first. Patients benefiting clinically at 1 year may continue treatment after a case-by-case review with the Sponsor.

The overall end of study occurs at the last visit or last scheduled procedure for the last patient, unless the study is terminated earlier by Sponsor.

- Disease assessments: CT or MRI

- Physical examination, including neurological examination

- ECOG Performance status

- Height and weight

- Vital signs

- Laboratory tests (hematology, chemistry, coagulation, thyroid function, urinalysis, and as applicable, additional microbiological studies)

- Pregnancy test, if applicable

- 12-Lead ECG (triplicate)

- AEs/SAEs, graded according to CTCAE version 4.0.

- DLTs (dose-escalation only)

- Blood sampling for PK, ADA, [REDACTED]

[REDACTED]

Other Assessments:

Study Drug, Dosage, and Mode of Administration:

Camidanlumab tesirine is administered as a 30-minute intravenous (IV) infusion on Day 1 of each cycle.

Patients treated with camidanlumab tesirine as monotherapy, in the initial dose cohort will receive 20 μ g/kg Q3W and the highest dose possibly tested will be 300 μ g/kg Q3W.

Patients treated with camidanlumab tesirine in combination with pembrolizumab, in the initial dose cohort will receive 30 μ g/kg Q3W of camidanlumab tesirine. The highest dose possibly tested of camidanlumab tesirine in combination with pembrolizumab, will be the highest dose investigated and deemed safe, of camidanlumab tesirine as monotherapy.

Pembrolizumab at dose of 200 mg Q3W will be administered on Day 1 of each cycle starting from Cycle 1 onwards (dosing schedule 1). If unacceptable toxicity occurs during Cycle 1, dosing Schedule 2, where pembrolizumab administration may start at Cycle 2, may be investigated in new enrolled patients.

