Camidanlumab tesirine, at the starting dose of 30 μ g/kg, will be administered first for 2 cycles to perform its immunotherapy priming effect; pembrolizumab is intended to be given from the start to benefit of the potential synergistic effect seen in the non-clinical studies.

In order to minimize the dose levels to be investigated and start with a dose with potential antitumor activity, this study will investigate dose of camidanlumab tesirine in combination with pembrolizumab between 30 μ g/kg and the highest dose level of camidanlumab tesirine as monotherapy shown to be safe.

A sequential dosing regimen may be implemented to mitigate overlapping toxicities at the discretion of the DESC.

[figure not shown]

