6 TREATMENT

The study drugs are camidanlumab tesirine and pembrolizumab.

The study treatment refers either to camidanlumab tesirine as monotherapy or to camidanlumab tesirine in combination with pembrolizumab, as applicable.

The start of a Cycle is defined as the administration of any of the study drugs.

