6.5 Dose-Limiting Toxicities

For the dose-escalation of camidanlumab tesirine as monotherapy, a DLT is defined as any of the following events, which occur during the 21 days following the first study drug administration period of Part 1 (excluding the paired-biopsy cohorts), except those that are clearly due to underlying disease or extraneous causes.

For the dose-escalation of camidanlumab tesirine in combination with pembrolizumab, a DLT is defined as any of the following events, which occur during the 21 days following the first administration of pembrolizumab in Part 1, except those that are clearly due to underlying disease or extraneous causes.

A hematologic DLT is defined as:

Event	Severity
Febrile neutropenia or neutropenic infection	\geq Grade 3
Neutropenia lasting >7 days	\geq Grade 4
Thrombocytopenia	\geq Grade 4
Thrombocytopenia with clinically significant bleeding	\geq Grade 3
Thrombocytopenia requiring a platelet transfusion	\geq Grade 3
Anemia	\geq Grade 4
Anemia requiring transfusion	\geq Grade 3

A non-hematologic DLT is defined as:

Event	Severity
Hy's law case	Aspartate transaminase (AST) and/or alanine transaminase (ALT) $>3 \times$ upper limit normal (ULN) and bilirubin $>2 \times$ ULN, and without initial findings of cholestasis (serum alkaline phosphatase [ALP] activity $<2 \times$ ULN) and no other reason that could explain the combination of increased transaminases and serum total bilirubin, such as viral hepatitis A, B, or C, preexisting or acute liver disease, or another drug capable of causing the observed injury.
Hypersensitivity/infusion-related reaction (regardless of premedication)	\geq Grade 3. A Grade 3 hypersensitivity/infusion related reaction that resolves within 24 hours after onset with appropriate clinical management does not qualify as a DLT.
Radiculitis / Polyradiculopathy / GBS	\geq Grade 2
All other non-hematologic toxicity	\geq Grade 3

The following conditions **are not considered** DLTs:

Event	Severity
Fatigue	Grade 3 for \leq 7 days.
Diarrhea, nausea, or vomiting	Grade 3 in the absence of premedication that responds to therapy and improves by at least 1 grade within 3 days for Grade 3 events or to \leq Grade 1 within 7 days.
Alkaline phosphatase (ALP) and gamma glutamyl transferase (GGT)	Grade 3 ALP and GGT elevations, unless considered clinically relevant by the investigator.
Serum lipase or serum amylase	Grade 3 for \leq 7 days if without clinical signs or symptoms of pancreatitis.

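### If pembrolizumab first starts at Cycle 2 or later (Schedule 2), the replacement period and the DLT window do not overlap, so the DLT-evaluable set keeps patients never exposed to the combination and a cohort can fall short

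*Protocol*

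**What the plan says.** **DLT window.** For the combination, Protocol 4.1.1 states that the DLT "observation period for dose-escalation will start at the time of first administration of pembrolizumab" and closes 21 days later. Protocol 6.5 agrees: DLTs are listed events "which occur during the 21 days following the first administration of pembrolizumab in Part 1".

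**Schedules.** Schedule 1, the starting schedule, gives both drugs from Cycle 1. Schedule 2 is "Administration of camidanlumab tesirine for the first 2 cycles with concomitant administration of pembrolizumab in the second cycle", then pembrolizumab alone. Protocol 4.1.1 makes it a fallback: "Schedule 2 may be initiated if dose level -1 and dose level -2 used in Schedule 1 are presenting safety concerns". Section 6.4 also ties it to those two dose levels. The synopsis trigger names no dose level: "If unacceptable toxicity occurs during Cycle 1, dosing Schedule 2, where pembrolizumab administration may start at Cycle 2, may be investigated". Section 2.3.2 adds: "A sequential dosing regimen may be implemented to mitigate overlapping toxicities at the discretion of the DESC".

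**Replacement.** Protocol 5.5 replaces any Part 1 patient who discontinues within the first treatment cycle for a reason other than a DLT. Section 6 fixes when a cycle begins: "The start of a Cycle is defined as the administration of any of the study drugs". Under Schedule 2, Cycle 1 therefore begins with camidanlumab tesirine alone.

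**Analysis set.** Protocol 9.2 and SAP 4.1.2 start from all Part 1 patients who receive study drug. Among early leavers they remove only those who discontinue from the study during the DLT period without a DLT. Neither requires receipt of pembrolizumab or observation to the end of the window. SAP 4.9.1.2 reports DLTs on this set by dose level.

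**Decision rule.** Protocol 4.1.1 defines the MTD as the "highest dose level at which none of the first 3 treated patients, or no more than 1 of the first 6 treated patients" have a DLT.

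**The concern.** The three rules fit together when both drugs start on the same day. When pembrolizumab starts a cycle later, the DLT window moves with it, but the replacement period stays on Cycle 1. The analysis set does not address anyone who leaves before the window opens.

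DLT incidence in dose escalation is a primary endpoint (Protocol section 3). If the rules are applied literally under Schedule 2, its denominator includes patients with no time at risk, and a cohort can be left with fewer observed patients than 3+3 assumes. The first effect lowers the reported DLT proportion; the second leaves less information behind it.

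**Working it through.** The plan gives no figure of its own on this point, so there is nothing to reproduce. The check applies the rules to days and patients.

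**Inputs**
- Cycle length: 21 days (Protocol 4.2.2).
- C2D1 = Day 22 and C3D1 = Day 43 (SAP 4.7.1, Table 1).
- DLT window: 21 days from first pembrolizumab (Protocol 4.1.1, 6.5).
- Replacement: first cycle (Protocol 5.5).
- Full AE reporting: to 30 days after last dose (Protocol 8.2).

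**Step 1: overlap of the two periods**
- Schedule 1: pembrolizumab starts after a 0.5 h infusion and a 1 h gap, so the window shifts by 1.5 h. The window is 21 × 24 = 504 h, and 1.5/504 = 0.3%. The periods coincide for practical purposes.
- Schedule 2: replacement covers Days 1-21. The window runs from Day 22 to Day 22 + 21 = Day 43 (Day 42 if Day 22 counts as the first day). Overlap is 0 days under either count.
- Pembrolizumab starting inside Cycle 1: a Day 8 start gives Days 8-21, 14 days of overlap; a Day 15 start gives Days 15-21, 7 days. Zero overlap needs a start at Cycle 2 or later.

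**Step 2: patients without a DLT under Schedule 2**

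| Patient | Replaced (5.5)? | In DLT-evaluable set (9.2, SAP 4.1.2)? | Observation of the window |
|---|---|---|---|
| Stops in Cycle 1, never gets pembrolizumab | Yes | Yes: did not leave during the DLT period | None; it never opens |
| Leaves the study in Cycle 2 | Not required | No | Partial |
| Stops drug after the C2D1 dose, stays on study | Not required | Yes | Full: AE reporting runs to Day 22 + 30 = Day 52, past Day 43 |

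The first row's replacement entry is certain for a patient who leaves the study outright, for example by death. For a patient who only stops drug, it depends on what 5.5 means by discontinuing. After a single Day 1 dose, full AE reporting ends on Day 1 + 30 = Day 31, 12 days before Day 43. A patient who stops for a Cycle 1 toxicity also falls in the first row, because that event precedes the window and is not a DLT.

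**Step 3: size from counts**

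The intervals are two-sided 95% Clopper-Pearson, the exact method named in SAP section 4. The SAP plans no interval for DLTs; they are shown only for scale. With no events the upper limit is 1 - 0.025^(1/n).

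- One retained, never-exposed patient: 1/6 = 16.7% (0.4-64.1%) becomes 1/7 = 14.3% (0.4-57.9%), a fall of 2.4 points. With no DLTs, 0/3 (upper limit 70.8%) becomes 0/4 (60.2%).
- One excluded, unreplaced patient: 0/3 (upper limit 70.8%) becomes 0/2 (84.2%).

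**Step 4: pooling of schedules**

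SAP section 4 splits combination tables by dose level, and Table 5 of Protocol 6.4 gives one list of dose levels for all schedules. If a level were used under both, a hypothetical 2/6 (33.3%) under Schedule 1 and 0/3 under Schedule 2 would appear as (2 + 0)/(6 + 3) = 2/9 = 22.2%, from two different windows.

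**Frequency.** The documents give no loss rate by cycle. Protocol 1.3.4 reports that 8 of 44 monotherapy patients (18.2%) had no post-baseline evaluation because of death or clinical progression. Early loss does occur in this population, but that figure does not place it in Cycle 1 or Cycle 2.

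**The case against.** Schedule 2 is optional, and nothing in the documents says that it was opened. Opening the window at first pembrolizumab is a coherent choice for a combination DLT. The Dose-Escalation Steering Committee sets doses from safety findings in all patients as well as from DLTs (Protocol 4.1.3), and the stopping rules in 4.3.2 are not confined to the DLT window. Cycle 1 of Schedule 2 is camidanlumab tesirine alone, under a dose cap set by monotherapy experience (6.4). Section 5.5 sets a minimum and does not forbid replacing a Cycle 2 leaver. All of this stands. It limits the consequence, but it changes neither the written denominator nor the replacement rule.

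Three stronger readings are tempting and are not supported.

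- **Escalation would go wrong.** If a cohort were judged on 2 patients instead of 3, the chance of seeing no DLT at an assumed true risk of 20%, 30% or 40% would be (1-p)² = 64%, 49% or 36%, against (1-p)³ = 51%, 34% or 22%. No passage provides for such a decision. Section 4.1.1 counts treated patients, and no passage ties escalation to the DLT-evaluable set.
- **Lead-in toxicity is ignored.** Events before pembrolizumab are not DLTs by definition, but the committee sees them, and the SAP tabulates Grade 3 or higher TEAEs by dose level and lists all AEs.
- **Every schedule is affected because 5.5 and 9.2 word discontinuation differently.** Stopping drug is not automatically leaving the study (5.4.1). Under monotherapy or Schedule 1, however, a patient who stops after the first dose and stays on study has AE reporting to Day 31, past the 21-day window. Keeping that patient is reasonable. Only the ambiguity in 5.5 remains.

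**Conclusion.** The point holds conditionally. If Schedule 2, or another schedule with first pembrolizumab at Cycle 2 or later, is opened, the replacement period and the DLT window are disjoint. The rules as written then keep never-exposed Cycle 1 leavers as DLT-free and do not require replacement of Cycle 2 study leavers. A pembrolizumab start within Cycle 1 would give a partial mismatch; Schedule 1 and monotherapy are essentially unaffected.

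The size is one patient per occurrence: 14.3% in place of 16.7% when one such patient is added to a cohort of 6 with one DLT, or 2 evaluable in place of 3. Pooling across schedules matters only if a dose level is used under both. These results rest on a literal reading of 5.5, 9.2 and SAP 4.1.2 and on the SAP day grid without delays. How often they would occur cannot be stated. What is shown concerns the reported denominator and cohort completeness, not dose selection. Severity: minor.

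**What to change.** - Reconcile Protocol 5.5, 9.2 and SAP 4.1.2 with the schedule-specific DLT period in 4.1.1 and 6.5. DLT-evaluable should mean that the patient entered that period and either had a DLT or was observed to its end. Replacement should use the same period.
- State in 5.5 whether discontinuing refers to study drug or to the study. Do not automatically exclude patients who stop drug but are observed through the window.
- In SAP 4.9.1.2, show DLTs by schedule as well as by dose level.
- List separately, by dose level and schedule, the patients who stop for toxicity before first pembrolizumab. Otherwise the revised denominator would contain only patients who got through the lead-in and would hide lead-in intolerance.
- Reconcile the Schedule 2 trigger in the synopsis with 4.1.1 and 6.4, so that it is clear when these rules apply. Which trigger or window is clinically right is for the sponsor.

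**Cost.** Wording changes in both documents, one extra table split and one listing. If such a schedule is used, expect a few more replaced patients, smaller denominators per row, and a DLT rate that is conditional on reaching pembrolizumab and must be labelled so.
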